5.1.2.1 Collection

Optional biopsies will be collected at baseline (if a sample was not collected at screening) and at the end of cycle 2. Archival samples may be used if patient refuses biopsy.

Collection of biopsy should be guided by ultrasound, CT scan, or other method according to the location of the selected lesion using $a \le 18$ gauge needle to provide cores ideally of at least 20 mm in length or equivalent size. At least 2, ideally 4 core biopsies will be obtained. Fine needle aspiration and biopsy of bone lesions are not acceptable.

The first core will be stored in the Laboratory of Pathology. Remaining samples will be stored in the Laboratory of [name], [name]. In general, [name] ([contact]; email: [contact]), a biologist in [name] lab will pick up the samples. If she is unavailable, another biologist will do so.

5.1.3 Assessment of Mesothelin Expression over Time

Fresh tumor tissue collected at baseline (optional) will be compared to archival material in order to determine whether mesothelin protein levels change over time and with disease progression. Mesothelin expression will be assessed by the Laboratory of Pathology using immunohistochemistry. Immunohistochemical staining will be evaluated by a pathologist and scored based on the intensity of staining as weak 1+, moderate 2+, and strong 3+, and the percentage of tumor cells that are positive.

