• To determine the efficacy (objective response rate) of anetumab ravtansine in patients with advanced (Stage IIIb) or metastatic (Stage IV) mesothelin expressing lung adenocarcinoma.

Eligibility:

- Age >18 years.
- Histologically or cytologically confirmed previously treated unresectable mesothelin expressing advanced lung adenocarcinoma (stage IIIB or IV)
- Positive mesothelin expression in the archival tumor tissue, defined as the mesothelin membrane intensity score of 2+ or 3+ (on the 0-3 scale) expressed on the membrane of ≥10% of tumor cells.

- Should have received at least one prior platinum based chemotherapy and an immune checkpoint targeted agent. In addition, subjects with epidermal growth factor receptor [EGFR]-mutated and anaplastic lymphoma kinase [ALK]-translocated NSCLC should have received FDA-approved targeted therapies as appropriate.
- Normal organ function

Design:

- This is an open label, single center, phase I/II study of anetumab ravtansine in subjects with mesothelin positive lung adenocarcinoma.
- During the safety run-in portion of the study, de-escalating doses will be assessed to determine a recommended phase 2 dose (RP2D).
- During the phase 2 portion of the study, the (RP2D) will be assessed for objective response rate.
- During both portions of the study, anetumab ravtansine will be administered intravenously every 3 weeks until disease progression in the absence of clinical benefit, patient withdrawal or the occurrence of intolerable toxicities.
- Response assessments (imaging) will occur every 6 weeks for the first 6 months, then every 9 weeks until the end of year 2, then every 12 weeks thereafter.
- Up to 12 evaluable patients will be enrolled in the safety run-in portion of the study. Approximately twenty patients, including 6 from the safety run-in portion of the study, will be evaluated in the phase 2 portion of the study. The accrual ceiling will be set at 55 to accommodate screen failures (a 50% failure rate with regard to mesothelin expression) and inevaluable subjects.

TABLE OF CONTENTS

PRÉCIS	2
TABLE OF CONTENTS	4
1 INTRODUCTION	8
1.1 Study Objectives	. 8
1.1.1 Primary Objectives	8
1.1.2 Secondary Objectives	8
1.1.3 Exploratory Objectives	8
1.2 Background and Rationale	. 8
1.2.1 Lung cancer	8
1.2.2 Mesothelin	9
1.2.3 Anetumab ravtansine	11
1.2.4 Rationale for the study	17
2 ELIGIBILITY ASSESSMENT AND ENROLLMENT	17
2.1 Eligibility Criteria	17
2.1.1 Inclusion Criteria	17
2.1.2 Exclusion Criteria	19

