2 ELIGIBILITY ASSESSMENT AND ENROLLMENT

2.1 ELIGIBILITY CRITERIA

2.1.1 Inclusion Criteria

2.1.1.1 Subjects must have histologically or cytologically confirmed previously treated unresectable mesothelin expressing advanced lung adenocarcinoma (stage IIIB or IV) as confirmed by the Laboratory of Pathology, NCI

- **2.1.1.2** Subjects must have positive mesothelin expression in the archival tumor tissue, defined as the mesothelin membrane intensity score of 2+ or 3+ (on the 0-3 scale) expressed on the membrane of $\geq 10\%$ of tumor cells.
- **2.1.1.3** Subjects must provide sample of archival tumor tissue (tissue block preferred, at least 5 formalin-fixated, paraffin-embedded [FFPE] slides acceptable) collected any time before the general screening. A fresh biopsy will be collected if archival sample is unavailable or insufficient.
- **2.1.1.4** Subjects must have measurable disease, defined as at least one lesion that can be accurately measured in at least one dimension (longest diameter to be recorded for non-nodal lesions and short axis for nodal lesions) as ≥ 20 mm with conventional techniques or as ≥ 10 mm with spiral CT scan. See Section 6.3 for the evaluation of measurable disease.
- 2.1.1.5 Subjects with resected primary tumors who have documented metastases are eligible.
- **2.1.1.6** Subjects should have received at least one prior platinum based chemotherapy and an immune checkpoint targeted agent. Subjects with epidermal growth factor receptor [EGFR]-mutated and anaplastic lymphoma kinase [ALK]-translocated NSCLC should have received FDA-approved targeted therapies as appropriate.
- 2.1.1.7 Age ≥18 years. Because no dosing or adverse event data are currently available on the use of anetumab ravtansine in subjects <18 years of age, children are excluded from this study.

- **2.1.1.8** ECOG performance status ≤ 2 (see Appendix B).
- **2.1.1.9** Subjects must have adequate bone marrow function as assessed by the following laboratory test results:
 - Hemoglobin ≥ 9.0 g/dL or ≥ 5.6 mmol/L
 - Absolute neutrophil count (ANC) \geq 1,500/mm³ or \geq 1.5 x 10⁹/L
 - Platelet count $\geq 100,000/\text{mm}^3$ or $\geq 100 \times 10^9/\text{L}$
- **2.1.1.10** Subjects must have adequate kidney function, with serum creatinine <1.5 x ULN or calculated glomerular filtration rate (GFR) of > 45/mL/min/1.73 m2
- **2.1.1.11** Subjects must have adequate liver function as assessed by the following laboratory test results:

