2.2 SCREENING EVALUATION

Step 1: The following assessments may be performed as soon as the initial 1st line treatment cycles with platinum/pemetrexed are administered.

- NCI LP confirmation of diagnosis
- NCI LP determination of mesothelin expression
- Medical History and Physical Examination

Step 2: Once mesothelin expression and diagnosis are confirmed, then proceed with the following tests described below.

The following screening assessments will occur within 28 days prior to initiation of study therapy:

- Medical history and physical examination including vital signs
- ECOG Performance Status
- CT scan of chest, abdomen and/or pelvis and areas of known or suspected disease involvement; MRI may also be performed when appropriate
- FDG-PET scan
- Echocardiogram
- Electrocardiogram
- Viral markers HBsAg, anti-HCV, anti-HIV

The following screening assessments will occur within 21 days prior to initiation of study therapy:

- Ophthalmologic exam (within 3 weeks before start of study therapy)
 - Visual acuity (BCVA according to ETDRS, or Snellen, or Landolt C or other charts)
 - Measurement of ophthalmic pressure (IOP)
 - Dry eye test [Schirmer test]
 - Slit lamp

The following screening assessments will occur within 7 days prior to initiation of study therapy:

- CBC with differential; Acute Care Panel (sodium, potassium, chloride, bicarbonate, creatinine, glucose, urea nitrogen, eGFR); Hepatic Panel (alkaline phosphatase, ALT, AST, Total Bilirubin, Direct Bilirubin)
- PT, PTT
- Urinalysis
- β-HCG in women of childbearing potential

2.3 **REGISTRATION PROCEDURES**

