5.1.3.1 Collection

Samples collected at screening (archival) and baseline (optional) as described previously will be used for this analysis.

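### In 5.1.3 the archival specimen that qualified the patient is also the reference for change, so regression to the mean biases the comparison towards apparent mesothelin loss

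*Combined protocol and SAP*

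**What the plan says.** **Selection.** The Précis and 2.1.1.2 admit patients whose archival tumor shows a "mesothelin membrane intensity score of 2+ or 3+ (on the 0-3 scale) expressed on the membrane of ≥10% of tumor cells". The test is done at screening Step 1 (2.2: "NCI LP determination of mesothelin expression"), and the remaining screening follows only once expression is confirmed. Under 2.1.1.3 a fresh biopsy is taken if archival tissue is missing or inadequate.

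**Comparison.** Section 5.1.3 states that "Fresh tumor tissue collected at baseline (optional) will be compared to archival material in order to determine whether mesothelin protein levels change over time", and also with disease progression. Section 5.1.3.1 identifies the material: "Samples collected at screening (archival) and baseline (optional) as described previously will be used for this analysis". The table in 5.2 likewise lists the archival sample taken at screening.

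**Scoring.** In 5.1.3, "Mesothelin expression will be assessed by the Laboratory of Pathology using immunohistochemistry", and staining is "scored based on the intensity of staining as weak 1+, moderate 2+, and strong 3+, and the percentage of tumor cells that are positive". That sentence has no membrane restriction, no 2+ floor and no cut-off. It does not say whether the qualifying archival reading is reused or the archival tissue is read again.

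**Analysis.** Section 8 treats the biopsy work as exploratory, with descriptive summaries only. No test, sample size or decision rule is attached to this comparison, and 1.1.3 does not list it as an objective.

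**The concern.** One specimen does two jobs: it decides who enters, and it is the starting point from which change is measured. Patients whose archival reading was high partly by chance (staining, reading, or which part of the tumor was sampled) are kept. Patients whose reading was low by chance are screened out and never give a fresh sample for comparison. The fresh reading is not selected in this way, so on average it drifts back down. This is regression to the mean, and no biological change is needed to produce it.

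A descriptive summary does not protect against this, because the descriptive mean change and the count of patients now below the cut-off are themselves the biased quantities. The risk is one of interpretation. With few pairs, a handful of fresh samples below the cut-off could be taken as loss of the target over time, and so as evidence against archival tissue as a basis for selection, when that count is about what no change would produce.

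The unspecified scoring measure is a second, separate problem. Without one stated measure for both specimens, the result cannot be read in either direction.

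**Working it through.** The plan gives no figure for this comparison, so there is none to reproduce.

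**Inputs from the documents**
- Cut-off: membrane 2+/3+ in at least 10% of tumor cells (Précis, 2.1.1.2).
- Share failing the mesothelin test: about 50% (Précis, section 8). Section 8 ties this share to a level below 5%, not below 10%, so the pass rate at 10% could be under 50%.
- Nearly 25% of an earlier series had more than 25% of cells positive (1.2.2.1).
- Evaluable patients: up to 20, or up to 26 if the lower dose is selected (section 8). The fresh biopsy is optional, so there may be fewer pairs.

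**Assumptions, not in the documents**
- Two readings of an unchanged tumor are bivariate normal with correlation ρ. SD means the SD of the score over all screened patients.
- ρ = 0.9, 0.8, 0.7 as the main range; 0.95 and 0.5 as outer values.

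**Formulas.** With pass rate p, cut-off c = Φ⁻¹(1 − p), and selection on the first reading:
- mean change = −(1 − ρ) φ(c)/p
- share of second readings below the cut-off = 1 − P(both pass)/p

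At p = 0.5 these reduce to −(1 − ρ)√(2/π), with √(2/π) = 0.798, and to 1/2 − arcsin(ρ)/π.

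**Pass rate 50%**
- ρ = 0.9: −0.1 × 0.798 = −0.08 SD; 0.5 − 0.356 = 14.4% below
- ρ = 0.8: −0.2 × 0.798 = −0.16 SD; 0.5 − 0.295 = 20.5% below
- ρ = 0.7: −0.3 × 0.798 = −0.24 SD; 0.5 − 0.247 = 25.3% below
- Outer values: −0.04 SD and 10% at ρ = 0.95; −0.40 SD and 33% at ρ = 0.5

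If all of 20 patients gave a pair, the number expected below the cut-off with no change is 2.9, 4.1 or 5.1 for ρ = 0.9, 0.8 or 0.7.

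**Lower pass rate.** A logit-normal percent-positive scale, calibrated by assumption to 50% of patients below 5% and 25% above 25%, gives a pass rate of 39% at the 10% cut-off. The shares below the cut-off become 17.7%, 25.2% and 31.1%. In simulation (1,000,000 draws) the mean archival score among those selected is about 43%, and the apparent loss is 2.7, 5.4 and 8.0 percentage points. Over all screened patients the mean change is about 0, so the loss comes from selection alone.

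**If scoring were mixed.** Suppose archival tissue kept the strict score while fresh tissue got a looser one that multiplies the odds of a positive cell by an assumed factor. On the same percent scale at ρ = 0.8, the mean change goes from −5.4 points (same measure) to −2.2 (factor 1.25), +0.5 (1.5) and +4.7 (2.0). A looser fresh score therefore offsets the selection effect and can reverse it.

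**Independent second archival reading.** If all variation is staining or reading error, using a second reading as comparator brings the simulated mean change to about 0 (−0.08 to −0.04 points for ρ from 0.5 to 0.95). Heterogeneity within the tumor or between sites is not removed.

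**The case against.** The strongest reply is that this is a small, optional, descriptive comparison with no decision attached. A shift of 0.08 to 0.24 SD in 20 to 26 patients at most would be hard to tell from noise, and the documents do not link the result to any later selection rule. All of that stands, and it sets the severity. It does not remove the bias in the quantity to be reported, or make the below-cut-off count interpretable without a benchmark.

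A reader might go further and infer that archival and fresh tissue are scored on different scales, so that loss is bound to appear. The documents do not support this:
- Section 5.1.3 gives one scoring scheme for the whole assessment, from the laboratory that also does the screening test. What differs is the wording of the eligibility rule and of the scoring description.
- If a strict archival score were in fact set against a looser fresh score, the effect would run towards gain, so scale cannot be a reason to expect loss.
- The text fixes the same specimen, not the same reading. Its wording is compatible with scoring both specimens afresh for this analysis.
- The fall is an expected mean shift of unknown size, not a certain finding in a small sample.

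It is also fair to say that not every treated patient need have qualified on archival tissue. Those who qualified on a fresh biopsy may have no archival pair and do not belong in the comparison.

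**Conclusion.** The concern holds in a limited form. Because the qualifying archival specimen is also the reference, and only archival-positive patients can supply a pair, the comparison in 5.1.3 is biased towards apparent loss when both specimens are scored on one measure. With no true change, a 50% pass rate and ρ from 0.9 to 0.7, the expected fall is 0.08 to 0.24 SD, with 14% to 25% of fresh samples below the cut-off. The direction needs only imperfect reproducibility; the size rests on the assumed ρ and the normal model. If the archival tissue is re-read, the part due to reading error goes and the part due to tissue sampling stays.

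The second limb is an omission. Section 5.1.3 does not carry over the eligibility measure or say which archival reading is used. If measures were mixed, the sign of the net bias would be unclear.

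Severity is minor. The analysis is exploratory, and the response endpoint and the two-stage design are untouched.

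**What to change.** Amend 5.1.3 as follows.

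1. Score archival and fresh tissue on the eligibility measure: percent of tumor cells with membrane staining of 2+ or 3+. State which archival reading is used.
2. Estimate change from the archival scores of all screened patients, including screen failures, jointly with the available fresh scores. This is valid if selection depends only on the recorded archival score; it also needs the model to hold below the cut-off and the choice to have an optional biopsy to be unrelated to the fresh level once the archival score is known. At the least, report the number of fresh samples below the cut-off beside the number expected with no change over a stated range of ρ, and state the selection effect when interpreting the result.
3. Where spare slides exist, re-read archival tissue blinded, alongside the fresh sample, and use that reading as the comparator. Say that this removes staining and reading error but not within-tumor heterogeneity.
4. Exclude patients who qualified on a fresh biopsy and have no archival pair.

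**Cost.** Items 1, 2 and 4 need a few sentences, the percent score recorded for screen failures, and a little more analysis. Item 3 needs an extra stained section per pair. Since 2.1.1.3 accepts as few as 5 slides, some patients will not have one, which is why it is conditional.

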5.1.3.1 Collection

Samples collected at screening (archival) and baseline (optional) as described previously will be used for this analysis.

5.1.4 Assessment of Myeloid Derived Suppressor Cells (MDSC) in Subjects with Lung Adenocarcinoma

5.1.4.1 Sample collection

Samples will be collected at baseline prior to first dose of anetumab ravtansine and the end of cycle 2 and at the end of treatment. All blood samples will be taken by either direct venipuncture or an indwelling venous access. At each sample collection time, blood (30 mL) will be drawn into three 10 mL sodium heparin (green top) tubes.

The tube should be labeled with the following information:

- Subject ID Number
- Study Number
- Time and date of collection

-Specimen type: peripheral blood

5.1.4.2 Sample processing

The samples will be sent to NIH Flow Cytometry lab located at [name].

All specimens for flow cytometry will be scheduled in advance by contacting [name] [contact] and/or [name] [contact] by email. Peripheral blood samples should arrive no later than 1 pm to the flow cytometry laboratory on the day scheduled.

Specimens are received in the laboratory via escort or via delivery by someone from the clinical team. Specimens for delivery AFTER HOURS ONLY may also be placed in the secure specimen drop box located in Laboratory of Pathology 3N hallway. Peripheral blood specimens are collected in sodium heparin tubes, and are stored at room temperature until delivery.

The specimens should be delivered as soon as possible after collection, and cannot be evaluated if > 48 hours old.

Upon receipt in the flow lab, the sample will be checked for correct labeling with appropriate patient identifiers and specimen type (e.g. peripheral blood).

Test/assay	Sample	Type of tube (if applicable)	Collection point (within)	Location of specimen analysis
Anti-mesothelin humoral immune response	4 mLs blood	10 mL serum Separator	Baseline, C3D1, EOT	Clinical Pharmacology Program
Gene expression characterization of the immune landscape &	Optional tumor biopsy	NA	Baseline, C3D1	[name] lab

5.2 SAMPLE COLLECTION SUMMARY

Abbreviated Title: Anetumab ravtansine in lung CA *Version Date:* 01-11-18

Test/assay	Sample	Type of tube (if applicable)	Collection point (within)	Location of specimen analysis
Assessment of Mesothelin Expression Over Time	Archival sample and optional tumor biopsy	NA	Archival sample collected at screening, and on study biopsies collected for Gene expression characterization study	Laboratory of Pathology
Assessment of MDSC	30 mL blood	Three 10 mL sodium heparin tubes	Baseline, C3D1, EOT	NIH Flow Cytometry Lab

5.3 SAMPLE STORAGE, TRACKING AND DISPOSITION

Samples will be ordered in CRIS and tracked through a Clinical Trial Data Management system. Should a CRIS screen not be available, the CRIS downtime procedures will be followed. Samples will not be sent outside NIH without IRB notification and an executed MTA.

5.3.1 Clinical Pharmacology Program

Upon arrival in the Clinical Pharmacology Program (CPP), OCD, CCR, NCI, all samples are barcoded, with data entered and stored in Patient Sample Data Management System (PSDMS), also known as *Labrador*, the system utilized by the CPP. This is a secure program, with access to the PSDMS system limited to defined CPP personnel, who are issued individual user accounts. PSDMS creates a unique barcode ID for every sample and sample box, which cannot be traced back to patients without PSDMS access. The data recorded for each sample includes the patient ID, name, trial name/protocol number, time drawn, cycle, time point, dose, material type, as well as box and freezer location. There are patient demographics that can be obtained to correlate with the samples through PSDMS. For each sample, there are notes associated with processing method (delay in sample processing, storage conditions on the ward, etc.)

Barcoded samples are stored in barcoded boxes in a locked freezer at either -20°C or -80°C according to stability requirements. These freezers are located onsite in the CPP and offsite at NCI Frederick Central Repository Services in Frederick, MD. Samples will be stored until requested by the researcher assigned to the protocol. All requests are monitored and tracked in PSDMS. All researchers are required to sign a form stating that the samples are only to be used for research purposes associated with this trial (as per IRB approved protocol) and that any unused samples must be returned to the CPP.

Following completion of this study, samples will remain in storage as detailed above. Access to these samples will only be granted following IRB approval of an additional protocol, granting the rights to use the material.

5.3.2 Laboratory of [name]

This study will follow storage, handling and labeling procedures to ensure that security, confidentiality and sample integrity are maintained. All samples (blood or tissue) are tracked by distinct identification labels generated by Labmatrix that include a unique patient identifier and date of specimen collection. Thus samples will be de-identified of personal data, with access to personal data restricted to the study investigators.

Depending on specimen type, samples are stored in liquid nitrogen, in monitored freezers/refrigerators at either -20 or -80°C according to stability requirements or in a slide cabinet in the research Laboratory of [name] ([name]).

5.3.3 Laboratory of Pathology

Tissues designated for clinical diagnostics are transported to the Laboratory of Pathology (LP) where they are examined grossly and relevant portions are fixed, embedded in paraffin and sectioned and stained for diagnostic interpretation. Unutilized excess tissues are stored for up to three months, in accordance with College of American Pathologists/Joint Commission on Accreditation of Healthcare Organizations (CAP/JCAHO) guidelines, and then discarded. Following completion of the diagnostic workup, the slides and tissue blocks are stored indefinitely in the LP's clinical archives. All specimens are catalogued and retrieved utilizing the clinical laboratory information systems, in accordance with CAP/JCAHO regulations. The use of any stored specimens for research purposes is only allowed when the appropriate IRB approval has been obtained. In some cases, this approval has been obtained via the original protocol on which the patient was enrolled.

